1.0 Study Summary

Study Title	A Comparison of Class II correction using the Carriere Motion Appliance versus an In-Office Sectional Appliance: Treatment Effects and Efficiency
Study Design	Pilot randomized clinical trial
Primary Objective	1. To evaluate total treatment time, in months, from the initial bonding appointment until a Class I molar relationship has been achieved and the appliance has been removed (T1) using either the Carriere Motion Appliance (CMA) or an in-office fabricated sectional appliance
Secondary Objective(s)	To evaluate secondary tooth movements (mm, degrees) and changes in skeletal measurements after Class II molar correction using the either the CMA or an in-office sectional appliance, by comparing lateral cephalometric radiograph measurements and digital study model measurements taken at the Initial Records appointment prior to treatment(T0) and immediately after removal of appliance – when a Class I molar relationship has been achieved (T1)
Research	Class II Correction Appliances: CMA vs. a sectional, in

Page 4 of 49

Intervention(s)/	office fabricated appliance
Investigational	
Agent(s)	
IND/IDE #	N/A
Study Population	12-17Y11M male and female patients
Sample Size	16 per treatment group (N = 32)
Study Duration for	5 months +/- 1 month
individual	
participants	
Study Specific	CMA= Carriere Motion Appliance
Abbreviations/	ss = Stainless-steel
Definitions	Sagittal first approach = correcting the antero-posterior occlusal relationship prior to the leveling and aligning phase of orthodontic treatment Class I molar relationship = The position of the mesiobuccal cusp of the maxillary first permanent molar occludes distally to the buccal groove of the mandibular first molar, and its distal buccal cusp is positioned in the embrasure between the mandibular first and second molars, when in centric occlusion Class II molar relationship = An occlusal relationship where the buccal groove of the mandibular first molar is positioned distal to the mesiobuccal cusp of the maxillary first molar, when in centric occlusion LFH = lower facial height

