2.0 Objectives*

2.1 Describe the purpose, specific aims, or objectives of this research.

Response:

The aim in this study is to explore the efficacy and efficiency of Class II molar correction with the sagittal first approach using either a sectional, in-office fabricated appliance or the CMA by measuring total treatment duration (in months) as well as comparing dental and skeletal measurements taken from lateral cephalometric radiographs obtained prior to Class II correction (T0) and immediately after removal of the appliance (T1). We will also be comparing secondary molar and canine rotational movements after Class II correction by comparing digital dental casts obtained at T0 and T1.

2.2 State the hypotheses to be tested, if applicable.

NOTE: A hypothesis is a specific, testable prediction about what you expect to happen in your study that corresponds with your above listed objectives.

Response:

1. There is no difference in mean duration (in months) of Class II molar correction when using a CMA or an in-office Class II correction appliance.

- 2. There is no difference in mean skeletal changes (in millimeters, degrees) after Class II correction using CMA or an in-office Class II correction appliance.
- 3. There is no difference in mean dental changes (in millimeters, degrees) after Class II correction using CMA or an in-office Class II correction appliance.

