3.0 Scientific Endpoints*

Describe the scientific endpoint(s), the main result or occurrence under study.

NOTE: Scientific endpoints are outcomes defined before the study begins to determine whether the objectives of the study have been met and to draw conclusions from the data. Include primary and secondary endpoints. Some example endpoints are: reduction of symptoms, improvement in quality of life, or survival. Your response should **not** be a date.

Response:

We hope to investigate whether the built-in features of the CMA will minimize total treatment time (in months) to achieve Class II correction to a Class I molar relationship when compared to an in-office sectional fabricated Class II correction appliance.

We also hope to investigate whether the CMA's built-in features will cause similar secondary effects after the Sagittal First approach of Class II correction when compared to an in-office sectional fabricated Class II correction appliance. These secondary effects include any additional dental or skeletal changes measured after Class II correction using the appliance aside from distalization of the maxillary buccal segments (canine to first molar).

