5.0 Study Design*

5.1 Describe and explain the study design (e.g. case-control, cross-sectional, ethnographic, experimental, interventional, longitudinal, observational).

Response:

This will be a pilot randomized clinical controlled trial including males and females with a unilateral or bilateral ½ cusp to full cusp Class II molar and canine relationship and mild to moderate crowding. The sample consists of adolescent patients who are receiving comprehensive full fixed appliance orthodontic treatment at the Postgraduate orthodontic clinic at the UBSDM. Subjects will be randomized into one of two treatment groups. Subjects will receive Class II correction prior to orthodontic treatment using either the CMA or an in-office fabricated Class II correction appliance. Lateral cephalometric radiographs and digital models will be taken at: T0 (initial records appointment) and T1(the appointment where the appliance is removed once Class II molar correction has been achieved). Patients in both treatment groups will use the same mandibular anchorage protocol (essix with 2 mm thickness and a button bonded to the buccal surface of the mandibular first molars). Elastic progression for both treatment groups will follow the protocol recommended by the CMA manufacturer (Force 1 Class II elastics (1/4, 6 oz) will be worn for 1 month, and Force 2 Class II elastics (3/16, 8 oz) will be worn for the remainder of Class II correction). Dental and skeletal changes will be measured using lateral cephalometric radiographs taken at T0 and T1, and rotational movements of the maxillary first molar and canine will be assessed using superimposition of the maxillary models taken at T0 and T1 using the e- model Compare 8.1 software by Geodigm. Treatment duration will be calculated (in months) starting on the date the appliance was bonded and ending on the date of appliance removal. Treatment duration and dental and skeletal movements will be compared between the two treatment groups.

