Both the CMA and the in office fabricated appliance will be utilized for Class II correction prior to comprehensive orthodontic treatment, and mandibular anchorage is necessary for both appliances. In our study we will be utilizing one of the CMA manufacturer's recommended mandibular anchorage protocols: a fabricated 2 mm essix retainer. An orthodontic button will be bonded to the buccal surface of the mandibular first molar on the affected side to provide mandibular anchorage for elastic use during Class II correction. Elastic

progression will follow the protocol recommended by the CMA manufacturer (Force 1 Class II elastics (1/4, 6 oz) will be worn for 1 month, and Force 2 Class II elastics (3/16, 8 oz) will be worn for the remainder of Class II correction) until a Class I molar relationship has been achieved.

- 1.1 Drug/Device Handling: If the research involves drugs or device, describe your plans to store, handle, and administer those drugs or devices so that they will be used only on subjects and be used only by authorized investigators.
- If the control of the drugs or devices used in this protocol will be accomplished by following an established, approved organizational SOP (e.g., Research Pharmacy SOP for the Control of Investigational Drugs, etc.), please reference that SOP in this section.

Response:

N/A

- 6.2 If the drug is investigational (has an IND) or the device has an IDE or a claim of abbreviated IDE (non-significant risk device), include the following information:
 - *Identify the holder of the IND/IDE/Abbreviated IDE.*
 - Explain procedures followed to comply with sponsor requirements for FDA regulated research for the following:

		Applicable to:	
FDA Regulation	IND Studies	IDE studies	Abbreviated IDE studies
21 CFR 11	X	X	
21 CFR 54	X	X	
21 CFR 210	X		
21 CFR 211	X		
21 CFR 312	X		
21 CFR 812		X	X
21 CFR 820		X	

Response:

N/A

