Isolation will then be removed and the patient will be instructed to wear the essix retainer 24 hours a day and to only take it out to eat and when completing hygiene methods. The patient will be given Force 1 Class II elastics (1/4, 6 oz) and will be instructed on how to place them from either the hook on the canine pad (CMA group) or the hook on the canine bracket (in-office appliance group) to the button on the mandibular first molars. The patient will be instructed to wear the elastics 24 hours a day and to only remove them when eating and completing hygiene methods, and to change elastics daily.

The patient will be seen 1 month later and will be given Force 2 Class II elastics (3/16, 8 oz) and will be instructed to wear them using the same protocol for the remainder of their class II correction. The patient will be evaluated each month until a Class I molar and canine relationship has been obtained.

Once a Class I molar and canine relationship has been obtained, The CMA or in office appliance will be removed, and an intraoral scan and lateral cephalometric radiograph will be taken immediately after removal of the appliance(s) (T1). The

total duration (in months) of Class II correction, starting at the bonding appointment and ending at the T1 appointment will be recorded for each subject.

Superimposition & Data Analysis

Once T0 and T1 records are obtained, lateral cephalometric tracing and measurements will be completed and recorded by one operator (AN). Superimpositions will be constructed using T0 and T1 lateral cephalometric tracings. Initial cephalometric measurement (T0) will be subtracted from final cephalometric measurements (T1) for each value (Please see table in section 12.2 for a complete list of lateral cephalometric measurements and their descriptions).

Intraoral scan data will be collected with an iTero Element 3D Scanner. Digital models will be superimposed using the Best fit method described in a study conducted by Grünheid and Larson. Maxillary model superimpositions will be used to address the difference in maxillary first molar and canine rotational positions before versus after Class II correction (°). Mean values for all measurements (lateral cephalometric and digital model superimposition) will be calculated for each treatment group and statistical analyses will be ran using he Statistical Package for the Social Sciences (SPSS) to compare means.

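### The event that ends the primary duration and sets T1 is Class I molar in some sections and Class I molar and canine in others

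*Protocol*

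**What the plan says.** **Molar alone.** The primary objective in Section 1.0 measures time from bonding "until a Class I molar relationship has been achieved and the appliance has been removed (T1"), and the secondary objective takes T1 records "when a Class I molar relationship has been achieved (T1"). Section 5.1 defines T1 as "the appointment where the appliance is removed once Class II molar correction has been achieved". Section 6.1 continues the elastic progression "until a Class I molar relationship has been achieved". Two further places state no removal trigger but are worded to match: hypothesis 1 in Section 2.2 ("There is no difference in mean duration (in months) of Class II molar correction") and the endpoint in Section 3.0 ("to achieve Class II correction to a Class I molar relationship").

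**Molar and canine.** Section 12.1 states: "The patient will be evaluated each month until a Class I molar and canine relationship has been obtained". Its next paragraph removes the appliance, and takes the T1 scan and film, once both relationships are Class I. Section 21.2 lists the efficacy datum as the months needed to reach Class I at both molar and canine.

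**How duration is counted.** Section 5.1 counts it "starting on the date the appliance was bonded and ending on the date of appliance removal". Section 12.1 counts it from bonding to the T1 appointment, which is the removal visit. Section 12.2 collects that one duration and no date at which the molar was first Class I.

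**The concern.** Each patient contributes one duration, and it stops when the appliance comes off. The criterion for taking it off therefore decides what the primary outcome is. It also fixes when the T1 cephalogram and scan are taken, and so the time at which every secondary dental and skeletal change is measured.

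If Section 12.1 is followed throughout, the trial measures time to molar-and-canine correction while its primary objective and hypothesis 1 speak of molar correction. If some staff follow Section 5.1 and others Section 12.1, the endpoint is a mixture. Section 7.3 draws patients from the pools of twelve residents, and the protocol does not name who decides removal. Mixing is therefore possible, but it is not shown. With only the removal date collected, the molar-only duration could not be recovered afterwards.

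**Working it through.** **1. The protocol's own figure.** Section 19.2 gives 16 per group for 80% power, a 0.05 significance level and a standardized effect of 1.02366. A two-sided two-sample t-test with these inputs needs 16.0001 per group, and power at 16 per group is 0.8000. The figure reproduces and is not in dispute. Section 19.2 refers to time to Class II correction without saying molar, or molar and canine, so it does not settle the question.

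**2. The sections side by side.**

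| Section | What it governs | Criterion |
|---|---|---|
| 1.0, primary objective | End of primary duration, T1 | Molar, plus removal |
| 1.0, secondary objective | T1 records | Molar |
| 2.2, hypothesis 1 | Quantity tested | Molar (no removal trigger) |
| 3.0 | Endpoint | Molar (no removal trigger) |
| 5.1 | Removal and T1 | Molar |
| 6.1 | End of elastic phase | Molar |
| 12.1 | Monthly evaluation, removal, T1 | Molar and canine |
| 21.2 | Efficacy duration | Molar and canine |

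**3. Are the two criteria equivalent?** The inclusion criteria in Section 8.1 require a Class II relationship at both molar and canine, so the canine condition is unmet at entry for every patient. Take a patient whose molar is Class I at one monthly visit and whose canine is not. Section 5.1 allows removal and T1 at that visit; Section 12.1 does not. Section 6.1 ends elastic wear, while Section 12.1 keeps the appliance on and the evaluations running. The criteria agree only if the canine is Class I no later than the molar.

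**4. Size for an affected patient.** Evaluation is monthly, so the recorded durations differ by about one visit interval or more. One month divided by each average CMA duration cited in Section 4.1:

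- 1 / 4.28 = 23.4%
- 1 / 4.4 = 22.7%
- 1 / 4.6 = 21.7%
- 1 / 5.2 = 19.2%
- 1 / 6.3 = 15.9%

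Against the 5 months expected in Section 13.2: 1 / 5 = 20%.

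**5. What cannot be computed.** The protocol gives neither the frequency nor the length of any canine lag, and no standard deviation of duration. The effect on the group means, the between-arm difference or the power therefore cannot be derived.

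**The case against.** The best defence is that the measured quantity never changes: every section that operationalises duration runs from bonding to removal. A patient whose appliance comes off under Section 12.1 has reached Class I molar and had the appliance removed, so the primary objective is literally met. Section 12.1 is the only stepwise visit instruction, and the template note heading it asks for enough detail to replicate the study, which makes it the natural operating rule. The opening of Section 12.1 describes eligibility by the molar alone where Section 8.1 names molar and canine, so the authors may use molar as shorthand. Section 4.1 says the CMA moves the buccal segment as a unit, so the lag may be negligible. Finally, this is a 32-patient pilot in which either rule would apply to both arms.

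Part of this stands. The primary objective, read alone, is compatible with Section 12.1. The lag may be near zero, and no bias between arms is shown.

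The rest does not remove the conflict:

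- Section 5.1 ties removal to molar correction and cannot be read together with Section 12.1.
- A removal date always exists, but the rule that produces it differs.
- Template guidance is not a statement of precedence. If Section 12.1 does govern, then Sections 1.0, 2.2, 3.0 and 5.1 misdescribe what is measured.
- Loose wording at the start of Section 12.1 does not override the formal eligibility criterion, and Section 21.2 shows that the two-part wording is not a stray phrase.
- The remark about movement as a unit is background on the CMA only. The molar attachments differ: the CMA joint is designed to limit distal rotation, while the in-office wire is left long behind the molar so that it can rotate. Equal lag in both arms cannot be assumed, and unequal lag is not shown.

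**Conclusion.** The concern holds. Current operative text gives two non-equivalent definitions of the event that ends the primary duration and times all T1 records, and nothing ranks them. This must be fixed because it concerns the identity of the primary endpoint, not because of an estimated shift. For a patient whose canine corrects after the molar, the difference is about one month or more, or 16% to 23% of the cited CMA averages. That rests on monthly evaluation as planned and on removal taking place at those visits. How many patients would be affected is unknown and could be close to none. The sample size is not called into question by this point.

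**What to change.** Reconcile Sections 1.0, 2.2, 3.0, 5.1, 6.1, 12.1 and 21.2 so that one event defines the end of the primary duration and T1 everywhere. Which criterion governs appliance removal is for the investigators to decide.

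- **If removal waits for both criteria:** reword the objective, hypothesis and endpoint to match. State what counts as a Class I canine relationship, since Section 1.0 defines only the molar. At each scheduled monthly visit, record for each treated side whether the molar is Class I, so that the molar-only duration can be reported as well. That date will be known only to the nearest monthly visit.
- **If removal is on the molar alone:** change the molar-and-canine wording in Sections 12.1 and 21.2. The time a lagging canine would have needed with the appliance in place is then never observed, so a molar-and-canine duration cannot be reported.

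The cost is a wording amendment and, in the first case, one extra item per treated side at visits already planned.

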2.0 Objectives*

2.1 Describe the purpose, specific aims, or objectives of this research.

Response:

The aim in this study is to explore the efficacy and efficiency of Class II molar correction with the sagittal first approach using either a sectional, in-office fabricated appliance or the CMA by measuring total treatment duration (in months) as well as comparing dental and skeletal measurements taken from lateral cephalometric radiographs obtained prior to Class II correction (T0) and immediately after removal of the appliance (T1). We will also be comparing secondary molar and canine rotational movements after Class II correction by comparing digital dental casts obtained at T0 and T1.

2.2 State the hypotheses to be tested, if applicable.

NOTE: A hypothesis is a specific, testable prediction about what you expect to happen in your study that corresponds with your above listed objectives.

Response:

1. There is no difference in mean duration (in months) of Class II molar correction when using a CMA or an in-office Class II correction appliance.

- 2. There is no difference in mean skeletal changes (in millimeters, degrees) after Class II correction using CMA or an in-office Class II correction appliance.
- 3. There is no difference in mean dental changes (in millimeters, degrees) after Class II correction using CMA or an in-office Class II correction appliance.

3.0 Scientific Endpoints*

Describe the scientific endpoint(s), the main result or occurrence under study.

NOTE: Scientific endpoints are outcomes defined before the study begins to determine whether the objectives of the study have been met and to draw conclusions from the data. Include primary and secondary endpoints. Some example endpoints are: reduction of symptoms, improvement in quality of life, or survival. Your response should **not** be a date.

Response:

We hope to investigate whether the built-in features of the CMA will minimize total treatment time (in months) to achieve Class II correction to a Class I molar relationship when compared to an in-office sectional fabricated Class II correction appliance.

We also hope to investigate whether the CMA's built-in features will cause similar secondary effects after the Sagittal First approach of Class II correction when compared to an in-office sectional fabricated Class II correction appliance. These secondary effects include any additional dental or skeletal changes measured after Class II correction using the appliance aside from distalization of the maxillary buccal segments (canine to first molar).

4.0 Background*

4.1 Provide the scientific or scholarly background, rationale, and significance of the research based on the existing literature and how it will contribute to existing knowledge. Describe any gaps in current knowledge. Include relevant preliminary findings or prior research by the investigator.

Response:

The Class I Molar Relationship

Maxillary first molar position is a prominent clinical factor in orthodontic diagnoses and treatment. In Class I normal occlusion, the position of the mesiobuccal cusp of the maxillary first permanent molar occludes distally to the buccal groove of the mandibular first molar. The maxillary first molar is inclined mesially, and its distal buccal cusp is positioned in the embrasure between the mandibular first and second molars. ² Three

IRB Version: 5/6/19

positional factors play a role in maxillary first molar relationship with the opposing dentition. This includes the position of the maxillary first molar in the maxilla, the axial inclination of the maxillary first molar, and the rotation of the maxillary first molar along its long axis. If the maxillary first molar is not positioned in normal occlusion, it can result in an unbalanced occlusion that may be misdiagnosed as a tooth size discrepancy of the opposing dental arch. 83% of patients presenting with malocclusions present with a mesially rotated maxillary first molar. If the maxillary molar is rotated mesially, this allows for more space in the arch, which can affect the remaining occlusal relationships, including canine relationship on the affected side. A

The Class II Molar Relationship

A Class II molar relationship is indicated when the buccal groove of the mandibular first molar is positioned distal to the mesiobuccal cusp of the maxillary first molar, when in centric occlusion. According to the NHANES III survey, around twenty-two percent of children between the ages of 8 and 11 present with a Class II molar relationship. These individuals can have a variety of different skeletal maxillary and mandibular relationships as well as variations in other identifying features of malocclusion including spacing, overbite and overjet. These differences can lead to variation in the presentation of the soft tissue profile of individuals with a Class II molar relationship.

Skeletally, a retruded mandible is typically present in Class II individuals, however, the maxilla can be protrusive as well. Class II individuals can also present with a range of lower facial heights (LFH) from decreased, to normal, to increased. An orthodontist must take these variations into account when treating Class II patients. In order to address any anteroposterior and vertical discrepancies in Class II individuals, the most ideal time to treat Class II patients is during adolescence, when a patient is still growing.

In a clinical setting, Class II malocclusion is typically divided into 2 subdivisions. Class II Division 1 and Class II Division 2 patients differ in many anteroposterior and vertical aspects, according to cephalometric measurements. Common features of Class II Division 1 patients include at least one of the following characteristics: a Class II skeletal relationship with the maxilla and the maxillary teeth being anteriorly placed in relation to the cranium, the maxillary teeth being anteriorly placed only, underdevelopment of the mandible, posterior placement of a normal-sized mandible, the mandibular dentition being placed posteriorly in a normal sized mandible, or a combination of any of the above findings. Class II Division 1 patients will also have a reduced interincisal angle. The palate of Class II Division 1 patients is typically narrower with a greater distance between the molar and canine due to proclined anterior teeth.

Class II Division 2 patients generally show a Class II skeletal relationship and an increased interincisal angle with a skeletal deep bite.^{7,8} Some Class II Division 2 patients may also present with a more narrow arch.³

Carriere Motion Appliance

The Carriere Motion Appliance (CMA) is a relatively new appliance that was introduced by Luis Carrière in 2003. The CMA is used to correct Class II (Division 1 and 2) or Class III dentoalveolar malocclusions and achieve a Class I occlusal relationship prior to the leveling and aligning phase of treatment (this method is referred to as the Sagittal First approach). Correcting occlusal relationships in a separate and initial phase eliminates the additional vectors of force that are elicited on the teeth when distalization is performed alongside archwire progression. ^{4,9} The CMA can be used to correct anteroposterior occlusal relationships in growing patients as well as adults. ^{4,10,9}

The CMA is made of a Nickle free stainless steel bar with a ball and socket joint, and it is bonded to the labial surface of the maxillary canine and maxillary first molar. 10,9 The device comes in 22 sizes to accommodate for the variation in distance between the buccal surface of the midpoint of the maxillary first molar and the buccal surface of the midpoint of the maxillary canine (or maxillary first premolar if the canine has not erupted). 10 Since the CMA is achieving Class II correction by applying force exclusively along the buccal segment in comparison to Class II correction after the leveling and aligning phase, when a patient is in a nonsegmented fixed orthodontic archwire that spans the entire maxillary arch, the inventors believe that the dentition will be less resistant to distalization forces.⁴ The canine pad is designed to allow for distalization of the canine without any tipping. 4,10,9 The distal portion of the canine pad is continuous with an arm that has a slight curve over the buccal surfaces of the two premolars and ends in a ball-and-socket joint with the molar pad. The ball has raised surfaces that correspond with depressions in the molar pad socket, which is designed to limit distal rotation of the maxillary first molar to -15-degrees along the longitudinal axis of the molar. The joint also designed to apply torque control of both the maxillary canine and maxillary first molar. 4,10,9

The molar pad is intended to induce 3 types of movement to correct maxillary first molar position. The first is to upright the maxillary first molar crown if it is mesially inclined. Next is distal rotation around the palatal root when the maxillary first molar is mesially rotated. When the maxillary first molar has been de-rotated, the shoulder of the posterior base of the molar pad is designed to contact the mesial arm of the appliance to prevent over rotation. The last built-in molar movement is distal displacement of the maxillary first molar without distal tipping of the crown. ^{10,9}

In order to minimize protrusion and proclination of the mandibular incisors during elastic wear, mandibular anchorage in combination with the CMA is necessary. ^{10,9} The type of mandibular anchorage used depends on the patient's skeletal and muscular characteristics. ^{9,11} This may include: a passive lingual arch from mandibular first molar to first molar, a Hamula lingual arch (a modified lingual arch designed with Hamula First Fit molar bands that contain occlusal stops on the mesial and distal portions of the bands with two segments of 0.021x 0.025" wire soldered to the stops and bonded to the occlusal surfaces of the mandibular premolars and second molars), a full mandibular fixed appliance (if the patient has a severe curve of Spee or mild mandibular crowding), a mandibular Essix retainer with small composite wedges bonded to the buccal surfaces of molars and premolars, or Miniscrews between the first and second molars. ^{4,10,9,11}

Class II correction using the CMA requires elastic wear. For elastic wear, during the first month of treatment, 6 oz, 1/4" Class II elastics (elastics extending from a hook located on the canine pad to a button or bracket bonded to the mandibular first molar) should be worn, and should be changed daily. Following the first month of elastic wear, the 6 oz, 1/4" Class II elastics will be exchanged for 8 oz, 3/16" elastics. The 8 oz, 3/16" elastics should be worn using the same protocol as the first month of treatment, until Class II correction is achieved. 10 The elastic should be changed daily, and the duration of elastic wear during the day can vary depending on skeletal growth pattern. 10 A low mandibular plane angle case (measured on a lateral cephalometric radiograph) with good perioral muscular strength should be instructed to wear Class II elastics 24 h a day. In high mandibular plane angle cases (also measured on a lateral cephalometric radiograph) who have lighter perioral musculature, elastic wear can be limited to only 14 h per day and should include mostly nighttime wear. 9,11 Patient compliance is generally greater in the beginning of orthodontic treatment when the patient is still motivated versus later on in treatment when a patient may be fatigued, and thus compliance with Class II elastic wear with CMA has been shown to be greater than elastic wear at later stages in orthodontic treatment.¹⁰ The goal before removal of the appliance is to surpass an ideal Class I canine relationship into a superclass I relationship (distal incline of the maxillary canine is in contact with the mesial incline plane of the mandibular cuspid), because some relapse is expected during the leveling and aligning phase treatment. Once the CMA is removed, the canine to first molars should be coligated under the archwire using a 0.012" stainless steel ligature wire in a figure-8 fashion. 4,10

CMA induces distal rotational movement of the maxillary first molars around their palatal roots and produces a uniform distal force on the posterior segment (from canine to first molar) as a unit. Distalization occurs while simultaneously minimizing maxillary molar tipping and maxillary bicuspid anchorage loss. With proper anchorage control in the mandibular arch, treatment using the CMA claims to minimize mandibular

incisor proclination. The appliance also claims to minimize periodontal reaction, although reasoning for this has not been described. 9,10

CMA Treatment effects and Treatment Duration

Few studies have investigated the overall treatment effects of Class II correction using the CMA. Research available indicates that the CMA successfully treats a mild to moderate Class II molar and canine relationship prior to the leveling and aligning phase of treatment through molar distalization and changes in overbite and overjet. ^{4,10-12} Average reported duration of Class II correction using the CMA is 4-6 months. ^{13,14,15,16,17} No significant skeletal effects were reported in most studies after Class II correction with the CMA in growing patients. ^{13,14,17} However, one study reported a clinically significant increase in lower facial height (LFH), and a statistically significant restriction of maxillary growth at point A after treatment using the CMA. ¹⁵

Dental effects of the CMA include distal movement of the maxillary canine¹⁰⁻¹² with distal tipping, distal rotation, and extrusion.¹⁶ Reported movements of the maxillary first molar include distal movement with distal tipping and rotation. When comparing treatment effects of skeletal Class I and Class II patients with Class II malocclusion, an increase in mesial movement of the mandibular first molar and mandibular incisor proclination were the only measured differences observed after Class II molar and canine correction in skeletal Class II versus Class I patients. ¹⁶

Short-term side effects reported after CMA use include additional space distal to the maxillary lateral incisors, extrusion of maxillary canines, and exacerbation of arch length discrepancy in the mandibular arch. Protrusion and proclination of mandibular incisors was reported in studies using a lingual arch, fixed appliances, and an Essix retainer for anchorage. 12,13,14,16,17 Mandibular incisor proclination was more pronounced when treating skeletal Class II patients versus skeletal Class I patients. 16 Mandibular molar mesialization and extrusion was also reported in some studies as a side effect. 16,17 Side effects involving the maxillary first molars after distalization include only minimal distal tipping, which suggests that the appliance aids in maintaining upright position of the maxillary first molars. 14

There are a limited number of studies reporting treatment duration of Class II correction phase using the CMA. The appliance is more efficient for growing patients, but it is also effective for adults. ¹⁰ The CMA workbook states that Class II correction for adults takes an average of 5 months to complete, while children should achieve Class II correction in an average of 3 months. ¹⁰ All studies reporting duration of Class II correction were performed on adolescent patients or growing patients. One study reported 4.9 months for patients with skeletal Class I and 4.2 months for patients with skeletal Class II, with a combined average of 4.6 months.

¹⁶ Another study reported an average of 4.28 months, a third reported 4.4 months, and a fourth study reported an average of 5.2 months. ^{12,14,15} A fourth study reported 6.3 months for total Class II correction time when using a CMA. ¹³ When measuring combined total treatment time (CMA followed by fixed appliances) one study reported an average combined total treatment time be 32.3 months with a conclusion that the CMA is not an efficient way to treat Class II malocclusions. ¹³ However, a second study reported a total treatment time of 18.2 months (5.2 months for CMA and 13.0 months for the rest of the treatment duration), and a third reported an average combined treatment time of 17.6 months. ^{12,15}

One study measured long-term effects of patients treated with a CMA followed by functional fixed appliance. Results indicated minor changes in molar movement when comparing CBCT measurements taken after removal of the fixed appliance and at a 4-year follow up. However, the inclusion criteria for this study were subjects with a Class I skeletal relationship, and an Angle Class II relationship of at least ½ cusp. The significant changes measured were mesial crown tipping of the maxillary first molars and lingual crown torquing of the mandibular incisors.¹⁸

CMA From the Patient's Perspective

